6.1.4. Handling of Dropouts and Missing Data

Unless indicated otherwise, summary statistics will be reported for observed data only and missing data will not be imputed. Patients whose clinical response is unknown or not reported will be treated as non-responders.

6.1.5. Pooling of Investigative Sites

As this is a Phase 1b/2 study, no by-site analyses are planned.

6.1.6. Determination of Sample Size

Simon's two-stage designs ([Simon 1989](#)) will be used for Substudies 1 and 4 and Fleming's two-stage designs will be used for Substudies 3 and 5. At the time point of interim analysis and decision to transition from Stage 1 to 2, all data collected in Stage 1 patients will be used to inform the decision.

Should the required number of events (i.e., responses) be reached prior to full enrollment to Stage 1, the time point for decision to transition from Stage 1 to Stage 2 may be taken before the stage is fully enrolled.

If the required number of events (i.e., responses) is not reached at the time of full enrollment to Stage 1, further enrollment may be suspended to allow for all patients to be exposed to derazantinib or derazantinib-atezolizumab in combination for at least 3 months or until disease progression.

The use of such designs will limit the number of overall exposed patients to a maximum of approximately 98, should either derazantinib or derazantinib-atezolizumab in combination be ineffective in Stage 1 of all efficacy-estimating substudies, as compared to a maximum of approximately 246 patients if derazantinib or derazantinib-atezolizumab are considered to be effective in all cohorts.

Assuming an overall incidence of approximately 20% qualifying FGFR1–3 GAs ([Helsten 2016](#)), up to approximately 680 patients will be screened for FGFR1–3 GAs, depending on the extent of preexisting molecular testing. Assuming that pre-treatment with an FGFR inhibitor was based on a known FGFR GA status, no repeated testing is anticipated for the approximately 100 patients enrolled in Substudy 4.

6.1.6.1. Substudy 1

The null hypothesis that the true ORR is $p_0 \leq 0.21$ will be tested against a one-sided alternative. In Stage 1, 35 evaluable patients will be enrolled. If 7 or fewer patients with an objective response are observed in Stage 1, the cohort will be stopped. If 8 or more patients with an objective response (defined as a CR or PR) are observed in these 35 patients, an additional 39 patients will be enrolled, for a total of 74 patients. The null hypothesis will be rejected if 22 or more responses are observed in these 74 patients. The one-sided Type I error rate is 0.0463, and the power is 0.8001 when the true ORR is $p_1 = 0.34$ and higher than the ORR of 32.2%, the highest reported value for an FGFR inhibiting treatment in mUC patients ([Balversa USPI](#)).

The ORR of 21% for the null hypothesis reflects the lower range of ORR seen in recent clinical studies of UC patients with FGFR Gas inhibitors ([Loriot 2019](#), [Necchi 2018](#), [Pal 2018](#)).

6.1.6.2. Substudy 2

This is a safety run-in using a modified rolling-six design including up to 24 patients in two dose cohorts. If none or 1 of six patients in the dose-level 1 cohort (200 mg derazantinib QD plus 1,200 mg atezolizumab Q3W) experiences a DLT in Cycle 1, dose level 1 will be considered tolerable. The dose-level 1 will then be expanded by additional 6 patients (expansion cohort for dose level 1) to further characterize the safety and tolerability profile. In addition, the dose-level 2 cohort (300 mg derazantinib QD plus 1,200 mg atezolizumab Q3W) will start enrollment with an initial target sample size of 6 patients. If dose level 2 is considered tolerable, then dose level 2 will be expanded by additional 6 patients to further characterize the safety and tolerability profile of this dose level. The sample size may increase if there is a need to explore further intermediate dose levels.

The RP2D will be determined by a joint decision taken by the IDMC, Investigators, and the Sponsor in reviewing the aggregate of DLT and AE data, and considering efficacy data.

6.1.6.3. Substudy 3

The Fleming’s two-stage design sample size calculation is based on the assumption that first-line cisplatin-ineligible patients with advanced or metastatic mUC expressing FGFR1–3 GAs treated with 200 mg BID derazantinib in combination with 1200 mg atezolizumab Q3W will attain a clinically meaningful ORR of approximately 45%, which is similar to that obtained with erdafitinib and cetrelimab ([Moreno 2020](#)), or rogaratinib and atezolizumab ([Rosenberg 2020](#)), in combination for this patient population, and is considered the benchmark by oncology experts. An ORR of 25% (estimated mean ORR with immune checkpoint-inhibiting monotherapy available for cisplatin-ineligible patients) is not considered sufficiently effective to warrant further clinical investigation. Using a Fleming’s two-stage design, a total sample size of 36 is required to test a null hypothesis of $H_0: \pi \leq 0.25$ versus an alternative hypothesis of $H_a: \pi \geq 0.45$ with a one-sided target significance level of 0.05 and target power of 80%, where π is the true proportion of successes. This design results in an exact type 1 error rate of 0.046, an exact level of power of 81%, and an average sample size of 27 patients under H_0 and 31 under H_1 .

Table 2 summarizes the required samples sizes and required responses to either accept or reject H_0 .

Table 2: Sample size and required responses of proposed two-stage Fleming design (Substudy 3)

	Sample size		Responders to accept H_0		Responders to reject H_0	
	N	n	%	n	%	
Stage 1	18	4	22.2	10	55.6	
Stage 2	36	13	36.1	14	38.9	

6.1.6.4. Substudy 4, Cohorts 4a and 4b

For both cohorts within Substudy 4, the null hypothesis that the true ORR is $p_0 \leq 0.07$ will be tested against a one-sided alternative. In Stage 1 of each cohort, 16 evaluable patients will be enrolled. If 1 or fewer patients with an objective response are observed in these 16 patients, the cohort will be stopped. If 2 or more patients with an objective response are observed, an additional 34 patients will be enrolled for a total of 50. The null hypothesis will be rejected if seven or more responses are seen in these 50 patients. Type I error rate is 0.0448 and power is 0.8027 when true ORR is $p_1 = 0.20$.

The ORR of 7% for the null hypothesis reflects the ORR reported based on literature of retrospective data and/or small cohorts of uncontrolled studies ([Di Lorenzo 2015](#), [Soga 2010](#)) for FGFR1–3 GA expressing UC patients treated with third or fourth-line single-agent chemotherapy with prior progression following platinum-containing chemotherapy, immune-checkpoint blockade and/or FGFR inhibitor treatment.

6.1.6.5. Substudy 5

The Fleming’s two-stage design sample size calculation is based on the assumption that patients with mUC expressing FGFR1–3 GAs, after failure of prior platinum- or immune checkpoint- inhibitor-containing treatment, treated with 200 mg BID derazantinib will attain a clinically meaningful ORR of approximately 30%. This is similar to that obtained with erdafitinib for this patient population, and considered the benchmark by oncology experts. An ORR of 10% is not considered sufficiently effective to warrant further clinical investigation.

Using a two-stage Fleming design, a total sample size of 26 is required to test a null hypothesis of $H_0: \pi \leq 0.1$ versus an alternative hypothesis of $H_a: \pi \geq 0.3$ with a one-sided target significance level of 0.05 and

target power of 80%, where π is the true proportion of successes. This design results in an exact type 1 error rate of 0.039, an exact level of power of 81.9%, an average sample number of 18 patients under H_0 and of 21 under H_1 . Table 3 summarizes the required samples sizes and required responses to either accept or reject H_0 .

Table 3: Sample size and required responses of proposed two-stage Fleming design (Substudy 5)

	Sample size	Responders to accept H_0		Responders to reject H_0	
	N	n	%	n	%
Stage 1	13	1	7.7	5	38.5
Stage 2	26	5	19.2	6	23.1

6.2. Patient Characteristics

6.2.1. Patient Disposition

Patient disposition will be presented by substudy and cohort. In substudy 2 disposition will be presented by dose level. Tabulation will include the following:

- Number of patients screened
- Number (%) of patients dosed
- Number (%) in each patient population for analysis (including frequency of reasons excluded from PP population; distribution of major protocol deviations)
- Number (%) of patients who discontinued and reason(s) for discontinuation
- Number (%) of patients who completed the safety follow-up period (28 day and 90 day) and reasons for discontinuation
- Number (%) of patients who completed the survival follow-up period and reasons for discontinuation
- Treatment Phase and Study Duration

Patients excluded from the various analysis populations will be listed by substudy, cohort and dose level. Patients who discontinue will be listed by substudy, cohort and dose level with reason for discontinuation.

The number of patients by geographical region, country and site will be tabulated.

6.2.2. Protocol Deviations

Protocol deviations will be identified and categorized using the process outlined in the protocol deviation and non-compliance management plan. Review of protocol deviations for potential exclusion from analysis populations occurs at the monthly internal review meeting. The final decision will be made at the data review meeting with Basilea providing the final review and approval.

Major protocol deviations which are determined to potentially impact efficacy analyses will result in the removal of a patient from the PP population. For DZB-CS-201, the classification and categorization of protocol deviations per sponsor's definition are outlined in the Protocol Deviations Grading and Categorization Guidelines (Appendix 2 of the Protocol Deviation and Non-Compliance Management Plan) which is maintained in the collaborative workspace. The decision on which major protocol deviations warrant exclusion from the PP population will be determined prior to final analysis. Other deviations/scenarios may arise during the pre-lock data review that will be documented and reported.

Protocol deviations will be summarized for the safety/ITT population. The number and percentage of patients with a major deviation by type of deviation category will be presented by substudy and cohort (Substudies 1, 3,4 and 5) or by dose level (Substudy 2). In addition, all protocol deviations will be provided in a by-patient listing.

6.2.3. Background and Demographic Characteristics

Background and demographic characteristics will be summarized for the safety/ITT, mITT and PP populations. The following variables will be listed and summarized using both continuous and categorical descriptive statistics:

- Age
- Sex
- Ethnicity
- Race
- Height (cm)
- Weight (kg)
- BMI (kg/m²) – calculated as weight (kg)/height (m)²
- Child bearing potential
- Surgically Sterilized Status
- Menopausal Status
- ECOG at baseline

6.2.4. Smoking History

Smoking history data will be listed.

6.2.5. Tumor Molecular Status

For substudies 1, 3, 4 and 5, liquid and tissue tumor molecular status will be presented by substudy and cohort. For substudy 2, liquid and tissue tumor molecular status will be presented overall and by dose level. Tumor molecular status will be summarized for the safety/ITT population. The following variables will be summarized as categorical variables:

- Sample type (liquid/tissue)
- FGFR1 Status
- FGFR1 Gene Aberration Type
- FGFR2 Status
- FGFR2 Gene Aberration Type
- FGFR3 Status
- FGFR3 Gene Aberration Type
- Other FGFR
- Tissue PD-L1 Result
- Tissue PD-L1 Positive Result Category

- Expression results/range
- Score/cell type

6.2.6. Prior and Concomitant Medications and Procedures

Prior and concomitant medications and concomitant procedures will be summarized for the safety/ITT population.

Study drug will be considered as any dose of either derazantinib or atezolizumab. The first dose date will be the first dose either derazantinib or atezolizumab was received and the last dose date will be last dose either derazantinib or atezolizumab was administered.

Prior medication will be defined as any medication taken and stopped prior to the first dose of study drug. Concomitant medication is defined as any medication ongoing at time of first dose of study drug or taken after the first dose of study drug. A concomitant procedure is defined as any procedure ongoing at time of first dose of study drug or occurring after the first dose of study drug.

Medications or procedures missing both start and stop dates, or having a start date prior to the first dose of study drug and missing the stop date, or having a stop date on or after the last dose of study drug and missing start date will be counted as concomitant.

For partial dates, the following approach will be taken:

- If the start day is missing but the start month and year are complete, a medication or procedure will be excluded as being concomitant only if the start month/year is before the month/year of study drug administration and if the stop date (either full date, month and year if missing day, or year if missing month and day) is before study drug administration.
- If the start day and month are missing but the start year is complete, a medication or procedure will be excluded as concomitant only if the start year is before the year of study drug administration and if the stop date (either: full date, month and year if missing day, or year if missing month and day) is before study drug administration.

Prior and concomitant medications will be coded using the WHO Drug Dictionary (WHODRUG Global B3 Mar2019), and patient incidence will be tabulated by Anatomic Therapeutic Class (ATC) level 4 and preferred term (PT). Patients will be counted only once for each ATC or PT in the event that they have multiple records of the same ATC or PT in the database.

Concomitant procedures will be coded using Medical Dictionary for Regulatory Activities (MedDRA) version 22.0 or above and will be summarized by system organ class (SOC) and PT. Patients will be counted only once for each SOC or PT in the event that they have multiple records of the same SOC or PT in the database.

All prior and concomitant medications and procedures will be included in by-patient data listings.

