8.3.3 Prior and concomitant treatments

Medications and significant non-drug therapies used prior to and after the start of the study drug will be listed by patient and summarized by Anatomical Therapeutic Chemical term and by cohort.

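### SAP 6.2.6 anchors its missing-start-date rule for concomitant medication on the last dose, against the first-dose boundary in its own definitions; if coded literally, some on-treatment records go unclassified.

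*SAP*

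**What the plan says.** SAP 6.2.6 sets out two general definitions. For prior use: "Prior medication will be defined as any medication taken and stopped prior to the first dose of study drug". For concomitant use: "Concomitant medication is defined as any medication ongoing at time of first dose of study drug or taken after the first dose of study drug". Procedures have a parallel definition.

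A further sentence deals with missing dates and names three kinds of record to be treated as concomitant:

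- both dates missing;
- "having a start date prior to the first dose of study drug and missing the stop date";
- a record "having a stop date on or after the last dose of study drug and missing start date will be counted as concomitant".

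Two bullets then handle partial start dates. For a known year only, "a medication or procedure will be excluded as concomitant only if the start year is before the year of study drug administration", and the stop date must also precede study drug. The bullet for a known month and year works the same way.

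The section defines the first and last dose dates separately; for the latter, "the last dose date will be last dose either derazantinib or atezolizumab was administered". Protocol 8.3.3 divides the summaries at the start of study drug: "Medications and significant non-drug therapies used prior to and after the start of the study drug will be listed by patient".

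**The concern.** Whether a medication is concomitant should depend on whether it was still in use at or after the first dose. When the start date is unknown, the stop date is the only evidence, and the natural threshold is the first dose. The clause uses the last dose. A drug with no start date that stopped midway through treatment therefore fails the clause, and it also fails the prior definition because it did not stop before treatment began.

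The concomitant tables are where a reader looks for drugs that Protocol 6.4.2 prohibits or cautions against, such as systemic corticosteroids and QT-prolonging agents. If on-treatment records drop out, those tables undercount use.

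**Working it through.** The plan gives no figure to reproduce. The check compares the boundaries and then enumerates the rule.

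**Boundaries side by side**

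| Rule | Source | Anchor |
|---|---|---|
| Prior medication | SAP 6.2.6 | First dose |
| Concomitant medication | SAP 6.2.6 | First dose |
| Start known, stop missing | SAP 6.2.6 | First dose |
| Partial start date | SAP 6.2.6 | Study drug administration |
| Scope of summaries | Protocol 8.3.3 | Start of study drug |
| Start missing, stop known | SAP 6.2.6 | **Last dose** |

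Only the final row departs from the start of treatment. Because the section defines the two dose dates separately, last dose cannot be read loosely as first dose.

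**Enumeration**

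Assume, for illustration, a first dose on Day 1 and a last dose on Day 100. Take records with no start date and a known stop day between Day -30 and Day 130.

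- Prior: stop < 1.
- Clause as written: concomitant if stop ≥ 100.
- Clause with a first-dose anchor: concomitant if stop ≥ 1.
- General definition: concomitant if stop > 1, since the drug was then still in use after the first dose.

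| Stop day | Prior | Clause as written | Clause, first-dose anchor | General definition |
|---|---|---|---|---|
| -10 | Yes | No | No | No |
| 1 | No | No | Yes | Unclear |
| 2 | No | No | Yes | Yes |
| 50 | No | No | Yes | Yes |
| 99 | No | No | Yes | Yes |
| 100 | No | Yes | Yes | Yes |
| 120 | No | Yes | Yes | Yes |

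Results:

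1. Prior definition plus the clause as written: Days 1 to 99 are in neither class (99 stop days).
2. Prior definition plus a first-dose anchor: no stop day is unclassified.
3. Clause as written plus the general definition: Days 2 to 99 become concomitant. Only Day 1 stays unclear, because a drug stopped that day may have been taken only before the first dose.

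**What the clause adds.** If the general definition governs, the clause does no work for these records: every stop on or after the last dose already qualifies, apart from the trivial case of a patient whose first and last dose fall on the same day. Its threshold has an effect only on the restrictive reading, which is the one that loses records. On that reading the SAP also counts a record with no dates at all as concomitant but not one with a known mid-treatment stop date, which is the wrong way round.

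**The case against.** The strongest reply is that the SAP never says these records are not concomitant. The missing-date sentence adds cases and does not say only; where the section means to exclude, in the partial-date bullets, it says so. Nor can the sentence be exhaustive: a drug started on Day 30 with no stop date is not named in it, yet is plainly concomitant by definition. This stands. A reader might infer that the SAP as written removes these medications from both tables. The text does not support that, because the general definition in the same section captures a drug stopped after the first dose.

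Two other broader readings also fail. One is that all medications stopped during treatment are affected. Complete start dates fall under the definitions and partial ones under the bullets, so only a fully missing start date is in question. The other is that procedures fall out of two tables. The section specifies a summary of concomitant procedures but none of prior procedures, so a procedure could be lost from one summary only.

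The consequences are also limited. Protocol 5.3.2.9, 6.3 and 6.4 require start and stop dates to be recorded. Drugs begun on study for toxicity should therefore have a start date; long-standing medication is the likelier source of gaps. No efficacy, QT, hepatic or DLT analysis in the documents is specified to use the concomitant flag: SAP 6.4.5 relies on central ECG data and SAP 6.4.6 on laboratory values. By-patient listings are planned in SAP 6.1.1 and Protocol 8.3.3, so the records should remain visible there.

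None of this explains the last-dose anchor, for which the documents give no reason. A programmer could reasonably code the specific missing-date rule for records with missing dates.

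**Conclusion.** The clause is wrong as written, and the point is minor. It conflicts with the first-dose boundary used in the rest of SAP 6.2.6 and can lead to misclassification if coded as the whole rule for its records. On that assumption, every medication with a fully missing start date and a stop date from the first dose up to the day before the last dose is left unclassified, and any such procedure is missing from the concomitant summary. If the program applies the general definition as well, only a stop on the day of first dose is unclear.

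The number of records at risk cannot be derived from the documents and is probably small. The effect is confined to descriptive summaries; ORR, the stage decision rules and the adverse event analyses are untouched.

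**What to change.** In the missing-date sentence of SAP 6.2.6, replace last by first in the clause for a missing start date, so that a record with no start date counts as concomitant when its stop date is on or after the first dose of study drug. This also settles a stop on the day of first dose. Check that the derivation program for the concomitant flag, for both medications and procedures, follows the amended text.

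The cost is one word in the SAP and, if the program was coded literally, one condition in the code. No data collection or other analysis changes.

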5.3.1.4 Prior and concomitant medications

All non-antineoplastic medications or significant non-drug therapies (including herbal medicines) taken within 30 days of the Screening visit must be documented for each patient in the eCRF.

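### The SAP's partial-date rule counts some medications and procedures as concomitant although they are known to have stopped before the first dose

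*SAP*

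**What the plan says.** SAP 6.2.6 gives two definitions. For prior use: "Prior medication will be defined as any medication taken and stopped prior to the first dose of study drug". For concomitant use: "Concomitant medication is defined as any medication ongoing at time of first dose of study drug or taken after the first dose of study drug". Procedures count as concomitant on the same terms as medications.

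The section then handles incomplete dates. Three patterns with a wholly missing date count as concomitant: both dates missing; a pre-dose start with no stop; and no start with a stop on or after the last dose.

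Two bullets cover partial start dates. With the day missing, "a medication or procedure will be excluded as being concomitant only if the start month/year is before the month/year of study drug administration", and the stop must also precede study drug administration. With day and month missing, "a medication or procedure will be excluded as concomitant only if the start year is before the year of study drug administration", and again the stop must precede it. In each bullet the two conditions are joined by *and* and introduced by *only if*, so both must hold.

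The classification feeds patient-incidence tables: medications by ATC level 4 and preferred term, and procedures by system organ class and preferred term. All records also go into by-patient listings.

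**The concern.** Under the definitions the stop date alone separates prior from concomitant use. The bullets add a test on the start date. A record can therefore satisfy the definition of prior medication and still be counted as concomitant, and the programmer has two conflicting instructions for it. Nothing else in the SAP or the protocol settles which one applies.

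What is at stake is the accuracy of the concomitant tables. Each such record can place a patient in a row for a drug or procedure that never overlapped with study drug. A case that a clinical reader would notice is a systemic corticosteroid stopped before dosing, as exclusion criterion 27 (Protocol 4.3) requires in Substudies 3 and 4. If its start is recorded only as the dosing year, it would appear as on-study steroid use.

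**Working it through.** The plan gives no figure on this point, so the check applies the rule as written and compares it with the definition.

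**Inputs**
- Definition (SAP 6.2.6): prior if stop < first dose.
- Bullet 1 (start day missing): not concomitant only if start month/year < dosing month/year AND stop < dosing.
- Bullet 2 (start day and month missing): not concomitant only if start year < dosing year AND stop < dosing.
- The bullets refer to study drug administration. I read this as the first dose, the only reading that fits the definitions.

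**Rule against definition, first dose 20MAR2021 (illustrative dates)**

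| Start as recorded | Stop | Start test | Stop test | By the bullets | By the definition |
|---|---|---|---|---|---|
| --MAR2021 | 10MAR2021 | fails | met | concomitant | prior |
| --FEB2021 | 10MAR2021 | met | met | not concomitant | prior |
| 2021 only | 15FEB2021 | fails | met | concomitant | prior |
| 2020 only | 15FEB2021 | met | met | not concomitant | prior |

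Rows 1 and 3 conflict. Rows 2 and 4 agree.

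**Why the start test cannot help.** Start ≤ stop. If stop < first dose, then start < first dose, whatever part of the start date is missing. When the stop is known to be before dosing, the start test can only change a correct classification into a wrong one.

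**More information gives a worse answer.** A record with no start date at all and a pre-dose stop is not among the three wholly-missing patterns counted as concomitant, so it stays prior by definition. Add the dosing year as its start and bullet 2 makes it concomitant.

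**Rough size, under assumptions that are not document figures.** Protocol 5.3.1.4 requires non-antineoplastic medications "taken within 30 days of the Screening visit must be documented for each patient in the eCRF", and the screening window is 28 days (Protocol 5.2.1.3). Suppose that all starts lie 1 to 58 days before dosing (30 + 28 = 58), that first doses are spread evenly over one calendar year, that every start/stop pair has equal weight, and that every stop is known and pre-dose. Pairs per dosing day: 58 × 59 / 2 = 1,711. Over 365 days: 624,515.
- Day missing: 56,354 / 624,515 = 9% called concomitant.
- Day and month missing: 557,786 / 624,515 = 89% called concomitant.

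Now restrict start and stop to at least 14 days before dosing, to mimic the 2-week steroid washout. Pairs per dosing day: 45 × 46 / 2 = 1,035. Over 365 days: 377,775.
- Day missing: 10,607 / 377,775 = 3%.
- Day and month missing: 332,925 / 377,775 = 88%.

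These are shares of partial-start records with a known pre-dose stop, not shares of all records. The start-window assumption pushes them upwards: the protocol collects drugs *taken* in the window, so long-standing drugs begun in earlier months or years also enter, and the rule classifies those correctly.

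**The case against.** The strongest defence is that the section leans towards concomitant whenever dates are incomplete, and that over-inclusion is an acceptable convention in a safety-related table. That is sound where the stop date is missing, or is partial and could fall on or after dosing. It does not cover a stop known to be before dosing, because there is then no uncertainty to resolve.

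Several limits on reach do stand:
- Complete start dates are unaffected. Protocol 6.3 asks for accurate start and stop dates for medications in the pre-screening window, so a known stop paired with a month-only or year-only start may be uncommon.
- A reader might infer from the short collection window that most pre-dose records are exposed. The documents do not support this. The bullets act only on partial starts falling in the dosing month or year, and the window is defined by use, not by start.
- A reader might also infer that washed-out steroids are widely misclassified. With the day missing, a compliant course would have to start and stop within the dosing month and at least two weeks before dosing, which needs a dose around mid-month or later and a short course. The steroid example is largely confined to year-only starts.
- Each patient counts once per ATC class or preferred term, so a misclassified record adds nothing if the patient also has a genuine concomitant record in that row.
- The by-patient listings still show the dates. Per-protocol exclusions follow the separate deviation process in SAP 6.2.2.

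**Conclusion.** The rule is wrong as written, and the point is minor. A record is misclassified when three things coincide: the stop is known to be before the first dose; the start date is partial; and the recorded start month (day missing) or year (day and month missing) is the same as that of dosing. Every such record is affected, but the documents do not give their number and it may be small. The 9% and 89% shares rest on the assumptions listed and serve only to show that the year-only bullet carries most of the exposure.

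The consequence is confined to the descriptive concomitant medication and procedure tables. No endpoint, analysis population, censoring rule or hypothesis test depends on the flag, and the documents give no ground for inferring any effect on efficacy conclusions. This is a desirable correction, not a necessary one.

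**What to change.** Replace both partial-date bullets in SAP 6.2.6 with one rule:

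*If the stop date (or, if partial, its latest possible date) is before the first dose of study drug, the record is not concomitant, regardless of the start date; otherwise it is concomitant.*

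Applied to the table above, rows 1 and 3 become prior and rows 2 and 4 do not change. The conservative default survives where it is justified: a stop known only to the dosing month or dosing year has a latest possible date on or after dosing and stays concomitant, and so does a record with no stop date. Saying *not concomitant* lets the rule serve procedures too, for which the section defines no prior category. Naming the first dose also removes the looser reference to study drug administration.

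The cost is a wording change in the SAP and a shorter derivation. No data collection or protocol amendment is needed.
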